8.3.3. Adverse Events of Special Interest

Adverse events of special interest (AESIs) for this program include:

- a. Hypoglycemia
- b. Severe, persistent hyperglycemia

- c. Pancreatitis
- d. C-cell hyperplasia and C-cell neoplasms
- e. Cardiovascular events
- f. Hypersensitivity reactions

If a, b, c, d, e, or f are reported, sites will be prompted to collect additional details/data on the specific eCRFs.

Hypoglycemia

Participants will collect information on episodes of hypoglycemia starting from Visit 3 (Week 0) until the last study visit (ET visit or Visit 801). Participants will be trained about signs and symptoms of hypoglycemia, how to treat hypoglycemia, and how to collect appropriate information for each episode of hypoglycemia in the study according to the SoA (Section 1.3). Site personnel will enter this information into the hypoglycemia eCRF at each visit.

Investigators should use the following definitions and criteria when diagnosing and categorizing an episode considered to be related to hypoglycemia (the BG values in this section refer to values determined by a laboratory or International Federation of Clinical Chemistry and Laboratory Medicine plasma-equivalent glucose meters and strips) in accordance with the 2020 ADA position statement on glycemic targets:

Level 1 hypoglycemia

Glucose <70 mg/dL (3.9 mmol/L) and \geq 54 mg/dL (3.0 mmol/L): Level 1 hypoglycemia can alert a person to take action such as treatment with fast-acting carbohydrates. Providers should continue to counsel participants to treat hypoglycemia at this glucose alert value.

Level 2 hypoglycemia

Glucose <54 mg/dL (3.0 mmol/L): Level 2 hypoglycemia is also referred to as documented or blood glucose confirmed hypoglycemia with glucose <54 mg/dL (3.0 mmol/L). This glucose threshold is clinically relevant regardless of the presence or absence of symptoms of hypoglycemia.

Level 3 hypoglycemia

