9.4.4. Safety Analyses

All safety analyses will be conducted using both the SS1 and SS2 to assess the safety parameters through 26 and 52 weeks, unless otherwise stated.

Study Intervention Exposure

Exposure to study intervention will be calculated for each participant and summarized by treatment group.

Adverse Events

Adverse events will be coded from the actual term using the Medical Dictionary for Regulatory Activities (MedDRA) and reported by preferred term and system organ class (SOC). Selected notable AEs of interest may be reported using high-level terms. All AEs and TEAEs, defined as post-baseline events that are new events or preexisting conditions that worsened in severity after randomization, will be listed by participant and visit. Information on treatment, actual term, preferred term, severity, seriousness, and relationship to study intervention will also be reported.

Summary statistics will be provided for incidence of TEAEs, SAEs, and study discontinuation due to AEs or death during the treatment period. Counts and proportions of participants experiencing AEs will be reported for each treatment group, and Fisher's exact test will be used to compare the treatment groups.

Summaries (if appropriate) of AESI defined in Section 8.3.3 will be generated.

Hypoglycemic Episodes

Section 8.3.3 contains definitions of categories of hypoglycemia. A listing of individual hypoglycemic episodes by participant will be presented. Summaries will include both incidence and rates of hypoglycemia for the ITT population excluding data after initiation of another antihyperglycemic therapy.

The incidence of hypoglycemic episodes will be summarized by each treatment group, by visit, as well as overall. Treatment differences in the incidence of hypoglycemic episodes will be assessed using Fisher's exact tests. Treatment differences in rates of hypoglycemic episodes will be analyzed using a generalized linear mixed-effects model assuming negative binomial distribution if data warrant; otherwise, the Wilcoxon rank-sum test will be used. The model will include treatment, pre-study OAM class, baseline HbA1c stratum (low and high), visit, treatment-by-visit interaction, and baseline hypoglycemia rate. The logarithm of days between visits will be included as an offset to account for possible unequal duration between visits and between participants.

Severe, Persistent Hyperglycemia

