**Table GBGQ.3.1. Populations and Analysis Sets**

Populations or Analysis Sets	Description
Entered	All participants who sign the ICF.
Randomized	All participants who are randomized to a treatment arm.
Nonrandomized	All participants entered, but not randomized to a treatment arm.
Intention-to-treat (ITT) Population	All randomly assigned participants who are exposed to at least 1 dose of study intervention for an assigned treatment arm. Participants will be included in the treatment group they were randomized to.
Efficacy analysis set for Period I (EAS1)	Data obtained during Treatment Period I (26-week) from the ITT population, excluding data after initiating rescue antihyperglycemic medication or discontinuing study intervention (last dose date + 7 days). In the event of a treatment error, participants will be analyzed according to the treatment they were randomly assigned to receive.
Safety analysis set for Period I (SS1)	Data obtained during Treatment Period I from the ITT population, regardless of adherence to study intervention or initiation of rescue antihyperglycemic medication.
Efficacy analysis set for Period I and II (EAS2)	Data obtained during Treatment Period I and II (52-week) from the ITT population, excluding data after initiating rescue antihyperglycemic medication or discontinuing study intervention (last dose date + 7 days). In the event of a treatment error, participants will be analyzed according to the treatment they were randomly assigned to receive.
Safety analysis set for Period I and II (SS2)	Data obtained during both Treatment Period I, II and safety F/U period from the ITT population, regardless of adherence to study intervention or initiation of rescue antihyperglycemic medication.

Abbreviations: ICF = informed consent form; F/U = follow-up.

Treatment Groups and Comparisons for Each Study Period and Analysis Population are defined as follows.

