**Table GBGQ.3.2. Treatment Groups and Comparisons for Each Study Period and Analysis Population**

Study Period	Analysis Population	Treatment Groups	Abbreviation	Comparisons When Applicable
Treatment Period I (Week 26)	EAS1 SS1	dulaglutide 1.5 mg dulaglutide 0.75 mg Total	DULA1.5 DULA0.75 TOTAL	DULA1.5 vs DULA0.75;
Treatment Period II (Week 52)	EAS2	dulaglutide 1.5 mg dulaglutide 0.75 mg Total	DULA1.5 DULA0.75 TOTAL	DULA1.5 vs DULA0.75;
Overall Period (Week 56)	SS2	dulaglutide 1.5 mg dulaglutide 0.75 mg Total	DULA1.5 DULA0.75 TOTAL	DULA1.5 vs DULA0.75;

Abbreviations: EAS[X]=Efficacy analysis set for Period X (1 or 2); SS[X]=Safety analysis set for Period X (1 or 2)

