**Discrete variables (binary)**

For **efficacy binary endpoints** (achieving HbA1c levels <7.0% or  $\leq 6.5\%$ ), multiple post-baseline time point will be analyzed using a longitudinal logistic regression with repeated measurements, (generalized linear mixed model (GLM)), without imputation. The model term includes

- treatment, baseline value, visit, the interaction of treatment-by-visit, and pre-study OAM class.

Proportion of responders (denominator, numerator, %) at each time point will be shown (no statistical tests). Missing data is excluded from the denominator.

If convergence issue happens, simple logistic regression (week 26 at interim DBL, week 52 at final DBL) will be used with model terms

- treatment, baseline value, and pre-study OAM class.

For **safety binary endpoints**, including AE rate and qualitative laboratory analysis, Fisher's exact test will be used, unless otherwise specified.

For analyzing incidence of hypoglycemic episodes, treatment differences in the incidence of hypoglycemic episodes will be assessed using Fisher's exact tests, unless otherwise specified. Treatment differences in rates of hypoglycemic episodes (week 26 at interim DBL, week 52 at final DBL) will be analyzed using a **generalized linear model** assuming negative binomial distribution if data warrant; otherwise, the Wilcoxon rank-sum test will be used. The generalized linear model will include

- offset, treatment, baseline hypoglycemia rate, pre-study OAM class, and baseline HbA1c stratum,

The logarithm of days during active treatment period (exposure in days divided by 365.25) will be included as the offset to account for possible unequal duration between visits and between participants.

Note that in the protocol **generalized linear mixed-effects model** was planned. However due to low rate of the events, a convergence issue happened. Therefore, analysis was changed from the multi-visit analysis to the single visit analysis.

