#### **4.1.1. General Considerations for Follow-Up Period**

No efficacy analysis will be conducted for follow-up period. Safety analysis will include all data in follow-up period, unless otherwise specified.

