#### **4.6. Safety Analyses**

All safety analyses will be conducted using both the SS1 and SS2 to assess the safety parameters through 26 and 52 weeks, unless otherwise stated.

In this study AESIs defined in the PROTOCOL (Section 8.3.3) are as follows:

- a. Hypoglycemia
- b. Severe, persistent hyperglycemia
- c. Pancreatitis
- d. C-cell hyperplasia and C-cell neoplasms
- e. Cardiovascular events
- f. Hypersensitivity reactions

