#### 4.6.3.3. Hypoglycemia

##### TFLs Related to Hypoglycemia

Analysis	Additional Information
Listing of Individual Hypoglycemic Episodes	
Listing of Severe/Serious Hypoglycemia Episodes	
Summary of Level 1 hypoglycemia: Glucose <70 mg/dL (3.9 mmol/L) and >= 54 mg/dL (3.0 mmol/L)	Overall Period
Summary of Level 2 hypoglycemia: Glucose <54 mg/dL (3.0 mmol/L)	Overall Period
Summary of Level 3 hypoglycemia: Severe hypoglycemia	Overall Period
Summary of Nocturnal hypoglycemia	Overall Period
Summary of Clinically significant hypoglycemia (Level 2 or 3)	Overall Period

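### The SAP does not carry over the protocol's cut-off of hypoglycemia data at another antihyperglycemic therapy, and no rule ties the rate model's counts to its exposure offset

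*SAP*

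**What the plan says.** **Protocol.** Section 9.4.4 sends safety analyses to SS1 and SS2 unless stated otherwise, and then does state otherwise for hypoglycemia: "Summaries will include both incidence and rates of hypoglycemia for the ITT population excluding data after initiation of another antihyperglycemic therapy". Section 9.4.1 mentions the same exclusion in general terms, as something that may be done. On collection, Section 8.3.3 says: "Participants will collect information on episodes of hypoglycemia starting from Visit 3 (Week 0) until the last study visit (ET visit or Visit 801".

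**SAP data rule.** Section 4.6 says: "All safety analyses will be conducted using both the SS1 and SS2", again subject to a proviso for exceptions. Table GBGQ.3.1 defines both sets as holding data "regardless of adherence to study intervention or initiation of rescue antihyperglycemic medication". Section 4.1.1 adds: "Safety analysis will include all data in follow-up period, unless otherwise specified". Neither Section 4.1 (discrete variables), nor the table list in 4.6.3.3, nor the subgroup analyses in 4.7.1.2 gives a hypoglycemia exception.

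**SAP rate model.** Section 4.1 replaces the protocol's by-visit mixed model with a single negative binomial model at Week 26 or Week 52, and explains why. The offset rule is: "The logarithm of days during active treatment period (exposure in days divided by 365.25) will be included as the offset". Section 4.6.1 ends exposure at permanent discontinuation of study drug or completion of the treatment period.

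**Declared changes.** Section 4.1 discloses the change of model. Section 4.9, the place for changes to protocol-planned analyses, is marked not applicable.

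**The concern.** A programmer who follows the SAP would count episodes that occurred on rescue insulin, or on the therapy given after study drug was stopped, toward the randomised dose. The protocol says these are to be left out. This affects both the Fisher tests of incidence and the rate model.

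A second problem is confined to the rate model. The protocol's offset was days between visits, so each count was paired with its own interval. The SAP's offset is exposure, and nothing says that counting stops when exposure stops. Participants who discontinue drug are meant to stay in the study on another glucose-lowering treatment (Protocol 7.1), so later episodes are collected.

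Hypoglycemia is the first adverse event of special interest listed, and its incidence is a named secondary safety endpoint in a trial meant to support approval of the higher dose. Its data window should be fixed before unblinding.

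**Working it through.** The plan states no figure for this point, so there is none to reproduce. The check compares the rules and then sizes the effect under assumptions.

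**1. What each rule does to each kind of participant**

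| Participant | Protocol 9.4.4 counts | SAP counts, by default | SAP offset |
|---|---|---|---|
| On drug throughout, no other therapy | All treatment days | Same | Same days |
| Rescue insulin, stays on drug (Protocol 6.5.1) | Stop at rescue | Continue | Continues |
| Stops drug, stays in study on other therapy | Stop at other therapy | Continue | Ends at discontinuation |

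In the second row, counts and offset agree but the protocol cut-off is broken. Restoring the cut-off without changing the offset would create a mismatch there. In the third row, the cut-off is broken and counts and offset also disagree.

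**2. Person-time effect of stopping**

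Assumptions: no true dose difference, a share d stops at week t, and the later episode rate is k times the on-drug rate.

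Per arm, SAP rate / on-drug rate = [(1−d)·52 + d·(t + k·(52−t))] / [(1−d)·52 + d·t], with t = 8:

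| k | d = 10% | d = 5% | Ratio, 10% vs 5% | Ratio, 5% vs 2.5% |
|---|---|---|---|---|
| 0 | 1.000 | 1.000 | 1.000 | 1.000 |
| 0.5 | 49.8/47.6 = 1.046 | 50.9/49.8 = 1.022 | 1.024 | 1.011 |
| 1 | 52/47.6 = 1.092 | 52/49.8 = 1.044 | 1.046 | 1.022 |
| 3 | 60.8/47.6 = 1.277 | 56.4/49.8 = 1.133 | 1.128 | 1.064 |

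With 10% stopping in both arms the ratio is 1.00, but each arm's rate is 0% to 28% too high.

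**3. Effect in a negative binomial fit**

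The fit moves further than person-time because it gives short-exposure participants more weight than their share of days. Assumptions: 390 and 195 participants, 0.3 episodes per year, gamma frailty with shape 0.5, treatment and offset only (no stratification terms), 1,200 simulated trials per case.

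- 10% vs 5% stopping at week 8: 1.014, 1.042, 1.081 and 1.277 for k = 0, 0.5, 1 and 3. The SD of the log ratio is 0.21, 0.21, 0.21 and 0.29. The largest shift is ln 1.277 = 0.245, and 0.245/0.29 = 0.84 SE.
- 5% vs 2.5%: 1.019, 1.030 and 1.103 for k = 0.5, 1 and 3.
- Counts and days matched: 1.003. Equal 10% stopping: 1.005.
- 10% vs 5% with frailty shape 2: 1.056 (k = 1) and 1.192 (k = 3). At 0.1 episodes per year: 1.062 and 1.195.

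These are not upper bounds. Take 15% vs 5% stopping at day 91 of 364, with a fivefold later rate. The person-time figures are 527.8/323.05 = 1.634 and 418.6/350.35 = 1.195, a ratio of 1.37. Then ln 1.37 = 0.31, slightly above the largest SE listed; no SE was computed for that case.

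**4. Rescue**

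Assume rescue at week 26 in 2% (1.5 mg) and 5% (0.75 mg).

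- SAP as written, rate tripled on insulin: (1 + 0.02·0.5·2)/(1 + 0.05·0.5·2) = 1.02/1.05 = 0.97.
- Protocol cut-off with the exposure offset kept: (1 − 0.02/2)/(1 − 0.05/2) = 0.990/0.975 = 1.015 (1.022 in the model fit).

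**5. Incidence (no offset)**

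P(at least one episode) = 1 − (1 + m/0.5)^(−0.5), where m is the expected count. This gives 0.209 for m = 0.3 (full year); 0.382 for m = 0.808 (stops at week 8, k = 3); and 0.043 for m = 0.046 (cut at week 8). Mixing at 10% and 5% stopping:

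- As written: 20.9% vs 20.9% (k = 1), or 22.7% vs 21.8% (k = 3).
- With the protocol cut-off: 19.3% vs 20.1%.

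Each window leaves the difference within 1 point of zero. In the tripled case the two windows are 0.9 + 0.8 = 1.7 points apart.

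**The case against.** The best defence is that silence is not removal. SAP 4.6 repeats the protocol's own default with its proviso, the SAP is based on the protocol, and table specifications sit in a separate document. On that view the protocol exclusion still governs and the SAP only lacks a cross-reference. This does not hold: the proviso needs something in the SAP to state otherwise, and nothing does. The permissive sentence in Protocol 9.4.1 is general, while 9.4.4 is the rule for this endpoint. Even if the sponsor meant to use that latitude, 9.4.1 requires a change of method and its justification to be described in the SAP.

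A second defence is that the reference to the active treatment period limits the counts as well as the offset. That is a natural reading and would remove the mismatch. The SAP does not say it, however, and episodes on rescue insulin would still be counted.

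Several counterpoints do stand.

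- Protocol 7.1 expects permanent discontinuation to be rare. Protocol 7.2 lists a need for another effective agent as a reason to leave the study, so fewer participants may be followed on other therapy than assumed here.
- The named endpoint is incidence, which has no offset.
- The protocol cut-off is not neutral. With unequal stopping it creates a small difference of its own (19.3% vs 20.1% above).

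A reader might also infer that follow-up episodes to Week 56 are set against exposure to Week 52, which would raise a completer's rate by up to 56/52 = 1.077 in both arms. The documents do not establish this. SAP 4.8 excludes follow-up data at the Week 26 lock, and 4.1 places the final rate at Week 52. Table GBGQ.3.2 does label the SS2 row "Overall Period (Week 56", but the same label on the hypoglycemia tables may only mean that they are not by visit. Nor was the change of model hidden: Section 4.1 discloses it.

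**Conclusion.** The point holds as a conflict between the SAP's default data rule and a stated protocol rule, together with an unlinked count and offset in the rate model. It should be corrected, but it does not threaten the trial's main conclusion: the primary HbA1c analysis is untouched.

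The likely effect is small. It is below one standard error in the simulated cases with 10% vs 5% or 5% vs 2.5% stopping, and incidence differences stay within 1 point of zero. All of this rests on assumed event, stopping and rescue rates, because the documents give none by arm. The overstatement of each arm's rate needs only that episodes continue after stopping. Bias in the rate ratio also needs stopping or rescue to differ by arm, and it can go either way. The documents do not support reading this as evidence that the dose comparison will be materially wrong.

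**What to change.** In SAP 4.1 and 4.6.3.3:

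1. Carry over the Protocol 9.4.4 exclusion for both incidence and rates, or declare the change of data rule and justify it, with an entry in Section 4.9.
2. For the rate model, count episodes from first dose to the earliest of the start of another antihyperglycemic therapy, the end of exposure, or Week 26 (first lock) or Week 52 (final lock). Set the offset to the log of exactly those days.
3. Name the end week of the incidence tables at the final lock, Week 52 or Week 56. The Week 26 lock is already settled by Section 4.8.
4. If an all-data rate on SS1 or SS2 is also wanted, label it as a second analysis and use observation days as its offset.

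Protocol 9.4.4 contains no exemption for short-term insulin given in acute situations. If the sponsor wants one, it is a separate choice that the SAP should state.

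The cost is SAP wording and one derived end date per participant. Medication start dates and the distinction between rescue and short-term insulin are already collected under Protocol 6.5, so no new data are needed.

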### **Time to event analysis**

The Kaplan-Meier product limit method will be used to estimate cumulative event-free survival rates. Figure will be created. Cox proportional hazards regression analysis will be used to compare hazard rates between treatments using Wald test. The model term includes treatment group, pre-study OAM class, and baseline HbA1c stratum. Median confidence interval will be derived by log-transformed Greenwood formula.

#### **4.1.1. General Considerations for Follow-Up Period**

No efficacy analysis will be conducted for follow-up period. Safety analysis will include all data in follow-up period, unless otherwise specified.

#### **4.1.2. Handling of Dropouts or Missing Data**

Depending on the estimand being addressed, different methods will be used to manage missing data. Description of the estimands can be found in Section [1.1.1](#).

##### **4.1.2.1. Handling of Dropouts or Missing Data**

For efficacy analysis relative to the estimand for continuous endpoints collected multiple times post-baseline, a Mixed-effects Model for Repeated Measures (MMRM) will be performed without explicit imputation. The description of MMRM can be found in Section [4.1.2.1.1](#).

For efficacy analysis relative to the estimand for continuous endpoints collected only once post-baseline (or at each timepoint), missing data including those as a result of intercurrent events will be imputed using Last Observation Carried Forward (LOCF). The description of LOCF can be found in Section [4.1.2.1.2](#).

The table below describes the planned imputation methods for efficacy endpoints.

**Table GBGQ.4.1. Imputation Techniques for Various Variables**

Type of Endpoints	Efficacy Endpoints	Missing Data Imputation Method (Analysis Method)
Continuos	Continuous endpoints at multiple post-baseline timepoints	No imputation (MMRM)
	Continuous endpoints collected only once post-baseline (or at each timepoint)	LOCF (ANCOVA)

Abbreviations: ANCOVA = analysis of covariance; LOCF = last observation carried forward; MMRM = mixed-effects model for repeated measures.

#### ***4.1.2.1.1. Mixed-effects Model for Repeated Measures (MMRM)***

Mixed-effects model for repeated measures analyses will be performed on continuous endpoints to mitigate the impact of missing data. This approach assumes missing observations are missing-at-random (missingness is related to observed data) and borrows information from participants in the same treatment arm taking into account both the missingness of data through the correlation of the repeated measurements.

The values subsequent to rescue medication use or treatment discontinuation will be made missing before applying the MMRM model. The MMRM model is described in Section 4.1.

#### ***4.1.2.1.2. Last Observation Carried Forward (LOCF)***

In this analysis, the values subsequent to rescue medication use or treatment discontinuation will be made missing. All missing values will be imputed using LOCF. If there is no post-baseline observation, then the patient will be excluded from the analysis.

## **4.2. Participant Dispositions**

Frequency counts and percentages of all participants screened, randomized, and receiving at least 1 dose of study intervention (dulaglutide 1.5 mg or 0.75 mg), will be presented by treatment arm.

In particular, following TFLs will be created:

- Summary of Analysis Population which includes (see definition in the GBGQ PROTOCOL Table 1)
  - entered patients
  - non-randomized patients
  - randomized patients
  - ITT population
- Listing of Analysis Population
- Summary of Patient Disposition Prior to Randomization which includes
  - number of patients who discontinued prior to randomization
  - reason for discontinuation (denominator is patients who discontinued prior to randomization)

- Summary of Patient Disposition by Visit
- Listing of the Screen Failures
- Summary of Patient Disposition which includes followings (All randomized population as denominator):
  - study disposition status
  - study treatment status
  - reasons for study discontinuation
  - reasons for study treatment discontinuation
- Listing of Patient Disposition
- Summary of Patient Allocation (by investigator)
- Listing of Date of Visit

A Kaplan-Meier analysis of time from randomization to premature discontinuation from study by treatment arm will be provided. Cox proportional hazards regression analysis will be used to compare hazard rates between treatments using Wald test. The model term includes

- treatment group, baseline value, pre-study OAM class, and baseline HbA1c stratum.

